2.1. Hypotheses

The efficacy of the recombinant, adjuvanted herpes zoster vaccine (Shingrix®) is high. We hypothesize that early innate signatures of vaccination should correlate with responses to, and predict the immunogenicity of, Shingrix® in older adults, independently of age.

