13.4.5 Analyses of Exploratory Endpoint(s)/Outcome(s)

Exploratory Endpoint 1. The innate immune response signatures are identified from traditional immune parameters, gene expression measured by RNA-seq experiment, and metabolomics data measured by LC/MS. The innate signatures will be identified for the two age groups separately. The traditional immune parameters, genes, and metabolites that change significantly over baseline after immunization are considered innate signatures.

Traditional markers will be tested using paired t-test or Wilcoxon test against D0, and significant markers will be considered part of the innate immune signature.

RNA-seq data will be preprocessed using Bowtie and Tophat, and FPKM (fragments per kilobase of exon model per million mapped reads) values will be calculated. Gene level comparison of D1, D4, D14 and D30 vs D0 will be conducted using DESeq to find the transcriptomics signature of vaccination.

Metabolomics data will be processed using packages apLCMS, XCMS, and xMSAnalyzer and generate data tables containing accurate mass m/z , retention time(s), intensity, coefficient of variation, and

related descriptive characteristics, including minimal information standards for metabolomics data. SAM(8) and similar methods will be used to detect differential abundance of features between D1, D4, D14 and D30 vs D0 to select metabolic innate signatures.

After each vaccination, the innate signatures that are correlated with the D30 antibody titers are considered correlation signatures of the innate immune responses. The correlation will be assessed using Spearman's correlation and the associated p-values.

Exploratory Endpoint 2. We will use paired t-test or Wilcoxon test to compare each immune parameter (changes in phenotype of T cell responses and the kinetics of these changes) between D7, D14 and D30 after vaccination and D0 for each dose of Zoster vaccine.

Exploratory Endpoint 3. We will use paired t-test or Wilcoxon test to compare each immune parameter (changes in the magnitude of activated B cells, antibody secreting cells and memory B cells and the kinetics of these changes) between D7, D14 and D30 after vaccination and D0 for each dose of Zoster vaccine.

Exploratory Endpoint 4. We will use paired t-test or Wilcoxon test to compare VZV serology between D14, D30, D180 and D270+ (optional visit) after vaccination and D0 for each dose of Zoster vaccine.

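### Section 13.4.5 lets gene and metabolite changes at D14 and D30 count as innate signatures and correlates them with the D30 titre, so adaptive or same-visit changes can be reported as innate correlates

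*Combined protocol and SAP*

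**What the plan says.** Section 13.4.5, Exploratory Endpoint 1, gives a general definition: "The traditional immune parameters, genes, and metabolites that change significantly over baseline after immunization are considered innate signatures". It names no latest day, cell type or pathway. The selection step is then described by type of data.

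- Metabolites: SAM and similar methods test "differential abundance of features between D1, D4, D14 and D30 vs D0 to select metabolic innate signatures".
- Genes: "Gene level comparison of D1, D4, D14 and D30 vs D0 will be conducted using DESeq to find the transcriptomics signature of vaccination".
- Traditional markers: "Traditional markers will be tested using paired t-test or Wilcoxon test against D0, and significant markers will be considered part of the innate immune signature". No days are named here. The endpoint wording in 3.4 and 13.2 covers D1, D3, D7, D14 and D30 after each dose.

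The next step is the correlation: "After each vaccination, the innate signatures that are correlated with the D30 antibody titers are considered correlation signatures of the innate immune responses". The test is Spearman's. Nothing requires a feature to be measured before the titre.

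Two other places bear on this. The hypothesis in 2.1 is that "early innate signatures of vaccination should correlate with responses to" the vaccine and predict its immunogenicity. The primary endpoint (3.2 and 13.2) ties innate signatures to D0, D1 and D7.

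**The concern.** An innate signature is meant to be an early response that comes before the adaptive response and helps to explain it. Under 13.4.5 a feature earns the label by differing from D0 at any listed day. RNA-seq is run on whole blood (section 9, item 3), so lymphocyte transcripts are in the sample, and no planned step separates them. A gene or metabolite that moves at D14 or D30 because B or T cells have expanded meets the definition as well as one that moves at D1.

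The correlation step adds to the problem. A D30 feature is compared with a titre from the same visit. An association there may be real, but it is concurrent and cannot show that an early response predicts a later one.

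Section 1.1 makes predictive signatures a key goal and 13.6 repeats the prediction claim. The correlation in 13.4.5 is the only analysis the plan describes that links innate signatures to the later antibody response. If early and late features share one list under one label, the list does not answer the question in 2.1.

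**Working it through.** **1. The days side by side.** Sources: the omics list in 13.4.5, the endpoints in 13.2, and nominal visit days. Lead time is 30 minus the feature day.

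| Day | Omics list in 13.4.5 | Primary endpoint | T- and B-cell endpoints (2, 3, 5, 6) | Serology (4) | Lead before D30 titre |
|---|---|---|---|---|---|
| D1 | yes | yes | no | no | 29 days |
| D3 | no | no | no | no | 27 days |
| D4 | yes | no | no | no | 26 days |
| D7 | no | yes | yes | no | 23 days |
| D14 | yes | no | yes | yes | 16 days |
| D30 | yes | no | yes | yes | 0 days |

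Two of the four omics days (D14 and D30) are adaptive readout days outside the primary endpoint's innate days. D14 still precedes the titre, so its problem is the label. D30 has both problems: the label and no lead time.

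**2. Reach of the rule by type of feature.** For metabolites it is explicit, because the sentence that lists D14 and D30 also calls the result innate. For genes it is indirect: the gene sentence speaks of a signature of vaccination, and the general definition then makes changed genes innate. For traditional markers it is weak. D14 and D30 enter only through the endpoint wording, and the markers may be only the innate assays in section 9, items 1 and 2.

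**3. The plan's own figures (13.7).** Correlation: n = 30, two-sided alpha 0.01, true r = 0.57, Pearson, 80% power.

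- Fisher z: power = Φ(atanh(r)·√(n − 3) − z) = Φ(0.6475 × 5.196 − 2.576) = Φ(0.789) = 78.5%.
- Adding the bias term r/(2(n − 1)) = 0.57/58 = 0.0098 gives 80.0%. Simulation of Pearson's test gives 79.4%.
- Paired t-test, 0.88 SD, alpha 0.0005: noncentrality 0.88 × √30 = 4.82, power 79.8%.

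The stated figures reproduce. The planned correlation test is Spearman's, however. By simulation its power at r = 0.57 is about 72%.

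**4. Illustration of the two steps together.** Assumptions: bivariate normal data, n = 30, the titre correlated with the feature's change from D0, a paired t-test for selection, and Spearman at unadjusted alpha 0.01. The documents give no change size or correlation for adaptive features, so a range is shown. A feature is labelled an innate correlate if it passes both steps. Percent of 20,000 simulated trials, as selection alpha 0.0005 / 0.01:

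| Change at D30 | r = 0.4 | r = 0.57 | r = 0.7 |
|---|---|---|---|
| 0.66 SD | 11 / 24 | 27 / 57 | 38 / 75 |
| 0.88 SD | 23 / 30 | 56 / 70 | 75 / 93 |
| 1.2 SD | 30 / 31 | 72 / 72 | 94 / 95 |

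As a rough check on the middle cell, treating the two steps as independent gives 0.798 × 0.72 = 0.57, against 56% simulated.

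**The case against.** The strongest reply is that this is one exploratory endpoint. The primary endpoint is confined to D0, D1 and D7, and the tests in 13.4.2 use only those days and D60, D61 and D67. The D14/D30 rule feeds neither them nor the safety analysis. That stands, and it sets the severity.

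Several stronger readings are tempting, and the documents do not support them.

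- A reader might infer that adaptive changes will be reported as early predictors. Section 13.4.5 uses neither early nor predict; those ideas come from 2.1 and 13.6. Each contrast is made at a named day, so the day of a feature is known. The rule permits the mislabelling but does not make it certain.
- A reader might take the 80% in 13.7 as the chance that such a feature is declared. That figure is Pearson power and leaves out the selection step.
- A reader might count three of five days as adaptive by using the endpoint's own days. That counts D7, which the primary endpoint treats as an innate day.
- A reader might expect same-day adaptive features to rank highest. Nothing in the documents shows this.

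Two further defences do not remove the point. Section 13.4.5 allows other approaches ad hoc, but that does not correct the definition. Section 13.7 says false discovery rate will be used in the actual analysis, which would change the percentages above. It guards against null features, however, and the features at issue truly change and truly correlate. Only their label is wrong.

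**Conclusion.** The point holds for genes and metabolites and is weak for traditional markers. Followed as written, 13.4.5 can report adaptive changes, or changes from the titre's own visit, as correlates of the innate response, and no other section prevents it. Such results cannot test the early-signature hypothesis in 2.1.

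The firm part of the size is the count: two of four omics days, one of them with zero lead time. The percentages only illustrate how easily such a feature could pass, and they rest on the assumed change sizes and correlations, on normality and on unadjusted thresholds.

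This should be fixed. It is not critical, because the analysis is exploratory. A reader might infer that the primary result is compromised; the primary test does not use the D14/D30 rule, so it is not.

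**What to change.** In 13.4.5, Exploratory Endpoint 1:

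1. Limit innate-signature selection to prespecified early days: D1, D3 and D7 after dose 1, and D61, D63 and D67 after dose 2. D1 and D7 match the primary endpoint. D3 is in the exploratory endpoint and the visit schedule, whereas D4 is not a scheduled visit.
2. Allow only features from those days as predictors in the titre correlation.
3. Flag D7 and D67 features as overlapping adaptive readouts, so that they can be read apart from the earlier days.
4. Report D14 and D30 (D74 and D90) changes, and their associations with the titre, in a separate table as later or concurrent changes.

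The cost is wording only, since blood is already scheduled on all these days. The signature lists will be shorter. The days should be fixed before the data are analysed, because a cut-off chosen afterwards would be post hoc.

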Blood samples will be collected at D0 (pre-vaccination) and D1, D3, D7, D14, D30, D60 (second dose of vaccination), D61, D63, D67, D74, D90, D180 and D270+ (optional visit) post vaccination to study innate and adaptive immunity responses. Samples from the different cohorts will be labeled to preserve the blind of the laboratory staff running the assays during the first phase of the analysis. Stool samples will be collected at baseline to assess the microbiome.

[figure not shown]

Figure 1: Study design

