3.4. Exploratory Endpoint(s)/Outcome(s)

- The changes in transcriptomics, metabolomics and immune cell populations between D0 (before vaccination) and D1, D3, D7, D14 and D30 after each dose of Zoster vaccine recombinant, adjuvanted, in both age groups.
- The changes in the phenotype of T cell responses and the kinetics of these changes between D0 (before vaccination) and D7, D14 and D30 after each dose of Zoster vaccine recombinant, adjuvanted, as well as D180 and D270+ (optional visit), in both age groups.
- The changes in the magnitude of activated B cells, antibody secreting cells and memory B cells and the kinetics of these changes between D0 (before vaccination) and D7, D14 and D30 after each dose of Zoster vaccine recombinant, adjuvanted, as well as D180 and D270+ (optional visit), in both age groups.
- The changes in VZV serology between D0 (before vaccination) and D14 and D30 after each dose of Zoster vaccine recombinant, adjuvanted, as well as D180 and D270+ (optional visit), in both age groups.
- The changes in specificity, magnitude and phenotype of VZV-specific (gE and other antigens) T cells and the kinetics of these changes between D0 (before vaccination) and 7, 14, 30 days after each dose of Zoster vaccine recombinant, adjuvanted, and at D180 and D270+ (optional visit), in both age groups.
- The changes in magnitude of VZV-specific B cells and the kinetics of these changes between D0 (before vaccination) and 7, 14, 30 days after each dose of Zoster vaccine recombinant, adjuvanted, and at D180 and D270+ (optional visit), in both age groups.
- Microbiome parameters in stool collected at baseline. These will be correlated to the immune responses to the Zoster vaccine to assess whether the stool microbiome may be related, and possibly influence immune responses.

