8.6. Visit Windows

Study visits should take place within the time limits specified below:

D0 (first dose of vaccination) D1, D3, D7 (+/-1), D14 (+/-2), D30 (+/-7), D60 (+7) (second dose of vaccine), D61, D63, D67 (+/-1 from second vaccination), D74 (+/-2 from second vaccination), D90 (+/-7 from second vaccination), D180 (+/-14 from first vaccination, for each scheduled visit. An optional visit at any time point past 9 months (D270 +) from first vaccination may also take place.

This is also indicated on the Table of Events.

9. Mechanistic Assays

1. Expression of cytokines and chemokines via FACS. This assay will detect the expression profile of cytokines and chemokines to determine the innate response to vaccination.
2. Analysis of innate immune responses using FACS to assess numbers of activated innate cell populations. This assay will detect innate cell population activation including DC subsets, monocyte subsets, and NK cells, since these cell subsets are known to play crucial roles in immune regulation.
3. Molecular signatures of vaccination using RNA-seq on 2 mL of whole blood. This assay will determine the changes in mRNA and miRNA expression in whole blood. Results will be interpreted with use the method Significance Analysis of Microarrays (SAM) to determine change over baseline.
4. Microbiome Analysis: Analysis of microbiome diversity in the stool samples will be performed by Illumina MiSeq V4 16S Sequencing. Sample preparation will involve quantification and normalization of genomic DNA, PCR amplification of V4 hypervariable region of the bacterial 16S rDNA gene, PCR product quantification and library construction. Illumina MiSeq V4 16S sequencing and Bioinformatics analysis will involve V4 hypervariable region paired-end amplicon sequencing (MiSeq: 2x250 cycles). Filtering and trimming of all sequencing data will be done and mapped to taxonomic databases to identify bacterial composition in samples.
5. Levels of VZV-specific IgG/IgA/IgM antibody titers in the plasma by ELISA. This antibody assay will be used to quantify the levels of VZV-specific IgG and IgA in the plasma. Positive results will be assessed by 2X the negative control wells.
6. Number of VZV-specific IgG/IgA/IgM plasmablasts via ELISPOT. This cellular assay will be used to quantify the number of VZV-specific and total IgG/IgA/IgM antibody secreting cells in the blood. Positive results will be assessed by > 5 spots per million PBMCs.

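### The RNA-seq and metabolomics comparisons name day 4, when no blood is drawn, and omit days 3 and 7; separately, the analysis set demands a D30 sample that the primary test never uses

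*Combined protocol and SAP*

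**What the plan says.** For transcriptomics, Section 13.4.5 (Exploratory Endpoint 1) states: "Gene level comparison of D1, D4, D14 and D30 vs D0 will be conducted using DESeq". For metabolomics it plans to detect "differential abundance of features between D1, D4, D14 and D30 vs D0 to select metabolic innate signatures".

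The endpoint these analyses serve has other days: "The changes in transcriptomics, metabolomics and immune cell populations between D0 (before vaccination) and D1, D3, D7, D14 and D30 after each dose". It carries the same days in the synopsis, Section 3.4 and Section 13.2.

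The sampling schedule in Section 3.1 reads: "Blood samples will be collected at D0 (pre-vaccination) and D1, D3, D7, D14, D30, D60 (second dose of vaccination), D61, D63, D67, D74, D90". The opening of Section 8, Section 8.4.1 and Appendix D agree. Section 8.6 sets the windows: "D0 (first dose of vaccination) D1, D3, D7 (+/-1), D14 (+/-2), D30 (+/-7), D60 (+7) (second dose of vaccine), D61, D63", then "D67 (+/-1 from second vaccination), D74 (+/-2 from second vaccination), D90 (+/-7 from second vaccination".

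Two statements on these analyses carry no days. Section 9, item 3 says of the RNA-seq data: "Results will be interpreted with use the method Significance Analysis of Microarrays (SAM) to determine change over baseline". Section 13.4.5 says that markers, genes and metabolites "that change significantly over baseline after immunization are considered innate signatures".

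On the analysis set, Section 13.4.1 limits the data analysis to people given at least one dose who have both a D0 and a D30 measurement. It does not say after which dose D30 is counted. Section 13.4.2, the primary test, refers to D1, D7, D61, D67, D0 and D60.

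**The concern.** The omics lists and the endpoint cannot both be followed. Taken literally, the D4 contrast has nothing to analyse, and the D3 and D7 omics samples fall outside the listed contrasts. The lists also name no dose-2 days, although the endpoint applies after each dose. With about 20,000 genes to be tested (Section 13.7), the contrast days should be fixed before the data are seen.

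This is an exploratory analysis, which limits the stakes. It is not wholly detached from the primary aim: Section 13.4.5 is where innate signatures are defined, genes and metabolites are part of that definition, and D7 is one of the days the primary endpoint names.

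The D30 rule does bear on the primary analysis. A participant with every sample the primary test needs, but no D30 measurement, would be left out of it.

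**Working it through.** **1. Days on which a scheduled draw may fall (Section 8.6).** D61 and D63 are taken as days 1 and 3 after dose 2. The D67, D74 and D90 windows are counted from the second vaccination.

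| | Permitted days after the dose |
|---|---|
| Dose 1 | 0, 1, 3, 6–8, 12–16, 23–37 |
| Dose 2 | 1, 3, 6–8, 12–16, 23–37 |

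D3 has no window and D7 is ±1, so scheduled draws jump from day 3 to day 6. After dose 2 they jump in the same way, from D63 to one day before D67. Day 4 is in neither row.

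**2. Listed days against endpoint days.**

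- Listed in Section 13.4.5: {1, 4, 14, 30}
- Named in the endpoint: {1, 3, 7, 14, 30}
- Listed but not in the endpoint: {4}, or 1 of 4 listed days. Over two platforms, 2 of 8 listed contrasts have no planned sample.
- In the endpoint but not listed: {3, 7}, or 2 of 5 endpoint days. Over two platforms, 4 of 10 dose-1 contrasts are unlisted.

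The platform counts repeat one list used twice; they are not independent errors.

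**3. D30 and the primary test.** Section 13.4.2 uses {0, 1, 7, 60, 61, 67}. Day 30 is not in that set, however its sentence is parsed. The primary endpoint names D0, D1 and D7, again without D30.

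**4. What a D30 exclusion could cost.** For a two-sided paired t-test, power = P(T > t₀.₉₉₅,ₙ₋₁), where T is noncentral t with n − 1 degrees of freedom and noncentrality d√n. The other tail is negligible. Section 13.7 states 80% power for n = 30, d = 0.66 and alpha 0.01. The noncentrality is 0.66 × √30 = 3.61 and the power is 79.7%, so the plan's figure reproduces.

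The documents give no missingness rate. The losses below are assumptions.

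| Excluded of 30 | n | Power at d = 0.66 | d detectable at 80% |
|---|---|---|---|
| 0 | 30 | 79.7% | 0.662 |
| 1 | 29 | 77.8% | 0.675 |
| 3 | 27 | 73.7% | 0.703 |

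The falls are 79.7 − 77.8 = 1.9 and 79.7 − 73.7 = 6.0 percentage points.

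**5. Two smaller mismatches.** Exploratory Endpoints 2 and 3 extend to D180 and D270+, but their tests in Section 13.4.5 stop at D30; those for Endpoints 4 to 6 do not. Section 11.1 gives D1, D3 and D30 as the visits the primary endpoints need, which omits D7.

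**The case against.** On the lists, D4 may simply be a slip for D3, which would reduce the error to one wrong label and one missing day. That is fair as to size, but the text does not say so and D7 would still be missing. The lists could also be read as days after either dose, since Section 13.4.5 uses D30 that way for the titer correlation. That reading is open but not stated. The general statements about change over baseline name no days, so they do not correct two explicit lists. The closing allowance in Section 13.4.5 for other statistical approaches does not settle the days either.

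On D30, Section 11.1 calls it a critical visit for the primary endpoints, which agrees with Section 13.4.1 and suggests a deliberate rule. D30 titers are also needed for the correlation analysis. But Section 11.1 leaves out D7, which both the endpoint and the primary test use, so it belongs to the contradiction and cannot resolve it.

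The practical loss may be small, and that point stands. D30 has a ±7 day window, and Section 8.5 allows a repeat visit after a failed draw. Anyone who leaves before D30 has no D60, D61 or D67 sample, so for the contrasts on those days the rule costs only people who miss D30 and then return.

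Section 13.4 plans imputation, and a rule based on available samples might seem to conflict with it. It need not: requiring both samples of a contrast still permits imputation of missing assay values within them. Imputation cannot supply a day on which nobody was to be sampled.

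**Conclusion.** The concern holds and should be fixed. The omics lists contradict the schedule and the endpoint: one of four listed days has no planned sample and two of five endpoint days are unlisted. This follows from the text alone, and the endpoint already gives the days, so it is a correction and not an open choice. It affects the RNA-seq and metabolomics lists only; the traditional markers in Section 13.4.5 are tested against D0 with no day list.

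The D30 requirement is also wrong for the primary test. Its effect depends on how many participants lack D30, which the documents do not give. The power range rests on assumed losses of 0 to 3 per cohort, and the true effect may be nil. The power figures in Section 13.7 are not in dispute.

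**What to change.** - **Section 13.4.5.** Replace both four-day lists with D1, D3, D7, D14 and D30 after each dose, giving the dose-2 days as D61, D63, D67, D74 and D90. State whether D0 or D60 is the comparator after dose 2.
- **Section 13.4.1.** Include in each primary contrast every dosed participant with both samples of that contrast. Keep the D30 requirement for analyses that use D30, such as the titer correlation, and say after which dose. Add that the imputation in Section 13.4 applies to missing assay values within those samples.
- **Minor.** Add D180 and D270+ to the tests for Exploratory Endpoints 2 and 3. Reconcile the visits in Section 11.1 with the days the primary endpoint names; how many visits to require is for the sponsor to decide.

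The cost is wording. Blood on D3, D7, D63 and D67 is already scheduled, so no visit or sample is added. The number of participants will vary slightly between contrasts, so each table must report its own n.

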1.1. Background and Scientific Rationale

Varicella zoster virus (VZV), a member of the Herpesviridae family, is known to cause a wide spectrum of disorders in an individual's lifetime, including chicken pox (varicella), herpes zoster (shingles) and central nervous system disease (myelitis, meningitis, encephalitis, etc.). Primary infection with VZV causes chicken pox, a self-limited viral exanthema of childhood leading to fever and disseminated skin lesions. Due to its neurotropic properties, VZV has the ability to remain latent in neurons of the dorsal root ganglia, autonomic ganglia and cranial nerves after primary infection, and potentially reactivate later in life causing herpes zoster (HZ).¹ Reactivation is due to a decreased VZV-specific cell-mediated immunity², and risk factors include older age and an immunocompromised state (HIV, lymphoma, leukemia, bone marrow transplant, solid organ transplant, and immunosuppressive medications, etc.). Other risk factors include: depression, Caucasian race, female sex, physical trauma, prior history of HZ, diabetes mellitus, and family history (particularly first-degree relatives).^{3,4,5}

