2.4. Exploratory Objectives

- To assess the specificity, magnitude, kinetics or phenotype of VZV-specific (gE and other antigens) T cells of the Zoster vaccine recombinant, adjuvanted.
- To assess the magnitude, kinetics of VZV-specific B cells of Zoster vaccine recombinant, adjuvanted.
- To identify innate immune signatures that correlate with the magnitude of the adaptive immune responses to the Zoster vaccine recombinant, adjuvanted.
- To determine the differences in specificity, magnitude, kinetics or phenotype of VZV-specific (gE and other antigens) T cells to the Zoster vaccine recombinant, adjuvanted between adults ≥ 70 and 50-60 years of age.

- To determine the differences in magnitude, kinetics of VZV-specific B cells between adults ≥ 70 and 50-60 years of age to the Zoster vaccine recombinant, adjuvanted.
- To collect stool for microbiome analysis.

3. Study Design

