13.4 Analysis Plan

Data from the study will be analyzed using the statistical software R. High-throughput data will be analyzed using appropriate methods, either by stand-alone software or modules in leading statistical software, e.g. the Bioconductor in the R framework. For cytokine data, missing values will be dealt with using multiple imputations. For gene expression and metabolomics data, nearest neighbor method and local least squares may be used to fill missing values. Unsupervised learning techniques such as PCA, PLSDA, clustering, and factor analysis will be used for the visualization and identification of global patterns. For descriptive endpoints, we will generate summary statistics, and visualize the data using histograms and boxplots when applicable. For the identification of innate signatures, the two age groups will be analyzed separately.

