13.7 Sample Size Considerations

For sample size consideration, we will use the alpha level of 0.01 for the immune parameters. Given less than 50 immune parameters will be tested, this alpha level translates to an expected count of false positives of <1, which is an acceptable level. For the gene expression data and for sample size consideration only, we will use the alpha level of 0.0005 to offset the effect of multiple testing. This means an average of one false positive for every 2000 null genes tested; given ~20,000 genes will be measured, this alpha level translates to an expected 10 false positives. We expect >100 genes will be truly differentially expressed. Thus among all genes called differentially expressed, the proportion of false positives will be <10%, which is an acceptable level in gene expression studies. We note this consideration is for sample size analysis alone. In actual data analysis false discovery rate (FDR) will be used.

For the traditional immune parameters, with 30 samples in a treatment group, we can reject the null hypothesis of equal means with 80% power if the true effect size (mean difference/sigma) is 0.66, using a two-sided paired t-test and the alpha level of 0.01. For the gene expression, the actual data analysis will be performed using the false discovery rate. For simplicity, for sample size consideration, we will consider the simpler case of a paired t-test. With 30 samples in a treatment group, we can reject the null hypothesis of equal means with 80% power if the true effect size (mean difference/sigma) is 0.88, using a two-sided paired t-test and the alpha level of 0.0005.

For unpaired test, with sample size of 30 per group, at the alpha level of 0.01, we can reject the null hypothesis of equal means with 80% power if the true effect size ((mean0-mean1)/sigma, assuming equal variance) is 0.91 using an unpaired two-sided t-test.

For a paired t-test, with the sample size of 30, at the alpha level of 0.01, we can reject the null hypothesis of no change with 80% power if the true effect size (mean difference/sigma) is 0.66.

For correlation analysis, with 30 samples in the treatment group, at the alpha level of 0.01, we can reject the null hypothesis of zero correlation with 80% power if the true correlation is 0.57 using a two-sided test for Pearson's correlation coefficient.

14. Identification and Access to Source Data

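### The innate correlation signatures are defined against the unadjusted titre 30 days after each dose, so pre-dose immunity is mixed into what is meant to be the response to that dose

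*Combined protocol and SAP*

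**What the plan says.** Under Exploratory Endpoint 1, section 13.4.5 first selects markers, genes and metabolites that change over baseline. It then defines a subset: "After each vaccination, the innate signatures that are correlated with the D30 antibody titers are considered correlation signatures of the innate immune responses". The method follows: "The correlation will be assessed using Spearman's correlation and the associated p-values". No D0 or D60 titre, fold-rise or partial correlation is named.

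The objective that this step serves is in section 2.4: "To identify innate immune signatures that correlate with the magnitude of the adaptive immune responses to the Zoster vaccine recombinant, adjuvanted". The serology endpoint in section 3.4 is worded as a change: "The changes in VZV serology between D0 (before vaccination) and D14 and D30 after each dose". Its own analysis (Exploratory Endpoint 4 in section 13.4.5) tests against D0, but that change is not carried into the correlation.

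Section 13.4 adds: "For the identification of innate signatures, the two age groups will be analyzed separately". Section 13.7 gives the planning figure for about 30 participants per analysis: "at the alpha level of 0.01, we can reject the null hypothesis of zero correlation with 80% power if the true correlation is 0.57", for a two-sided Pearson test.

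The schedule of events (Appendix D) has blood drawn on D0 and on D60, the two vaccination days.

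**The concern.** The plan refers to baseline where it wants it, both in selecting signatures and in Endpoint 4. The plain reading of this step is therefore that the titre enters as measured. That titre has two parts: the level before the dose and the rise after it. Only the rise is the response to the dose.

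For dose 1, the pre-dose part is antibody from earlier VZV infection. Section 1.1 notes that "VZV has the ability to remain latent in neurons of the dorsal root ganglia", and the ELISA in section 9 measures VZV-specific antibody in general, so it can read such antibody. For dose 2 the argument needs no infection history, because the level at D60 already includes whatever dose 1 raised.

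Two errors follow. A marker that tracks prior immunity, or the dose-1 response, can be reported as a signature of the dose in question. A marker that truly tracks the rise is harder to detect. False discovery rate control does not help with the first, because the association with the raw titre is real. It just does not concern the response to that dose. This step is also the planned test of the study hypothesis that early signatures predict immunogenicity (section 2.1).

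**Working it through.** **Inputs from the documents.** n = 30 per analysis (sections 13.4 and 13.7), two-sided alpha 0.01, detectable correlation 0.57 at 80% power (section 13.7), Spearman test (section 13.4.5).

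**Assumptions, not in the documents.** Log titre after the dose T = B + R, with B the pre-dose level and R the rise. B and R are normal and independent. The ratio k = SD(B)/SD(R) is 0.5, 1 or 2. A marker tied only to B correlates with it at q = 0.5 or 0.2.

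**1. The plan's own figure.** Fisher z: atanh(0.57) = 0.6475; times √(30−3) = 5.196 gives 3.365; minus 2.576 gives 0.789; power = Φ(0.789) = 0.785. With the bias term it is 0.800, and Pearson simulation gives 0.79. The stated 80% reproduces. The planned test is Spearman, for which simulated power at 0.57 is about 72%, so that is the fair reference below.

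**2. Dilution of a true response marker.** Correlation with the raw titre = 0.57/√(1+k²):
- k = 0.5: 0.57/1.118 = 0.51
- k = 1: 0.57/1.414 = 0.40
- k = 2: 0.57/2.236 = 0.25

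**3. Leakage from a prior-immunity marker.** Correlation with the raw titre = q·k/√(1+k²), although the correlation with the rise is 0:
- q = 0.5: 0.22, 0.35, 0.45
- q = 0.2: 0.09, 0.14, 0.18

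**4. Rates by simulation.** All are rank correlations at alpha 0.01. Partial Spearman conditions on B and uses one degree of freedom fewer. Independent runs agree to about one percentage point.

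| | k = 0.5 | k = 1 | k = 2 |
|---|---|---|---|
| True marker (0.57 with rise), raw titre | 57% | 32% | 9% |
| True marker, partial Spearman | 68% | 65% | 57% |
| Prior-immunity marker, q = 0.5, raw titre | 8% | 22% | 41% |
| Prior-immunity marker, q = 0.2, raw titre | 2% | 3% | 5% |

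With partial Spearman the prior-immunity marker is called in about 1 to 1.5% of trials in every one of these settings.

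**5. Sensitivity to independence.** If rise and pre-dose level correlate at −0.5 and q = 0.5, the raw-titre call rate is about 1%, 9% or 38%. Partial Spearman stays at about 1%. A plain change score would itself call that marker in about 9% of trials.

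**The case against.** Several points on the other side have force.

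- **The size is not known.** The documents give no titre SD and no marker–baseline correlation. At q = 0.2 the false call rate is 2 to 5%, and at k = 0.25 with q = 0.5 it is under 3%. This stands: the table is an illustration and not an estimate.
- **The spread of pre-dose antibody is inferred.** Section 1.1 describes latency and says nothing about antibody levels. Section 4.3 excludes prior shingles and prior zoster or varicella vaccine, which plausibly narrows the spread. This weakens the dose-1 argument. It does not touch the dose-2 argument.
- **Attained titre can be a legitimate target.** Section 2.1 speaks of predicting immunogenicity, and section 1.1 of predicting later protective responses. That supports reporting the raw-titre correlation, but section 2.4 asks for response magnitude.
- **The plan allows flexibility.** Section 13.4.5 closes by permitting alternative approaches. It names no baseline adjustment, and choosing the outcome after seeing the data is no cure.

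A reader might infer that dose-2 signatures cannot be attributed to dose 2 at all. The documents do not support that. Carry-over weakens the attribution by an amount that they do not let one determine. A reader might also take the marker side to be a change score. The plan uses change over baseline to select signatures, but does not say whether the change or the level enters the correlation.

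**Conclusion.** The point holds as a mismatch between the stated objective and the outcome variable. As written, the correlation answers which markers go with a high titre after the dose. The objective asks which go with a large response to it. No figure in the plan is wrong on this account.

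The direction is clear: a true marker loses power, and a prior-immunity marker can be called above the nominal 1%. The magnitude rests on the assumed SD ratio, the marker–baseline correlation and the independence of rise and pre-dose level, and ranges from slight to serious. The power loss does not depend on q, and adjustment recovers most of it. Reading D30 after dose 2 as the D90 visit is natural, but the text does not say so.

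This should be corrected before the titres are analysed. It is confined to one exploratory step. The primary analysis, the safety analysis and the serology tests against D0 are not affected.

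**What to change.** In section 13.4.5, Exploratory Endpoint 1, replace the correlation step with wording such as: *For each dose and age group, the association between each innate marker and the log2 antibody titre 30 days after that dose will be assessed by partial Spearman correlation, adjusting for the log2 titre immediately before that dose (D30 given D0 for dose 1; D90 given D60 for dose 2). The unadjusted correlation with the post-dose titre will be reported descriptively.*

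State that D90 is the 30-day visit for dose 2, and whether the marker enters as a level or as a change. Plain fold-rise should not be the sole replacement: step 5 shows that it can flag prior-immunity markers when the rise depends on the starting level.

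**Cost.** One degree of freedom per correlation. For dose 1 the change is wording only, since D0 is already a serology time point. For dose 2 it also needs D60 plasma run in the same ELISA, up to 60 samples (2 × 30), if this is not already planned. The blood is drawn, but the serology endpoint in section 3.4 does not list D60, so that time point should be added.
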